5.3 Subject Enrollment

Before subjects begin participation in any study-specific activities/procedures, Amgen requires a copy of the site's written institutional review board/independent ethics committee (IRB/IEC) approval of the protocol, informed consent form, and all other subject information and/or recruitment material, if applicable (see Section 11.3).

The subject or the subject's legally authorized representative must personally sign and date the IRB/IEC informed consent before commencement of study-specific procedures.

Each subject who enters into the screening period for the study (screening period begins after the subject signs and dates the informed consent form) receives a unique subject identification number before any study-related activities/procedures are performed. The subject identification number will be assigned by interactive response technology (IRT). This number will be used to identify the subject throughout the clinical study and must be used on all study documentation related to that subject.

The subject identification number must remain constant throughout the entire clinical study; it must not be changed after initial assignment, including if a subject is rescreened. This number will not necessarily be the same as the randomization number assigned for the study.

A subject is considered enrolled when the investigator decides that the subject has met all eligibility criteria and has been randomized into the study. The investigator is to document this decision and date, in the subject's medical record and in/on the Subject Enrollment Case Report Form (CRF).

The sponsor may monitor enrollment into the prespecified strata. Enrollment into any particular stratum may be paused to ensure the adequate representation of other strata in the study population, in line with study objectives.

Sites that do not enroll subjects within 6 months of site initiation may be closed.

Protocol Number: 20200195

Date: 15 April 2022 Page 33 of 99

5.4 Screen Failures

Screen failures are defined as subjects who consent to participate in the clinical study but are not subsequently enrolled in the study. A minimal set of screen failure information will be collected that includes demography, screen failure details, eligibility criteria, and any serious adverse events.

Individuals who do not meet the criteria for participation in this study (screen failure) may be rescreened. Refer to Section 8.1.1.

6. Study Intervention

Study intervention is defined as any investigational product(s), non-investigational product(s), placebo, combination product(s), or medical device(s) intended to be administered to a study subject according to the study protocol.

Note that in several countries, investigational product and non-investigational product are referred to as investigational medicinal product and non-investigational medicinal product, respectively.

A summary of the dosing and administration of each treatment is shown in Table 6-1 below.

6.1 Study Interventions Administered

6.1.1 Investigational Products

Protocol Number: 20200195

Date: 15 April 2022 Page 34 of 99

Table 6-1. Investigational Products

	Amgen Investigational Product: ^a Apremilast	Placebo			
Dosage Formulation	film-coated tablet; 10, 20, and 30 mg tablets in blister cards for double-blind, placebo-controlled period; 30 mg tablets provided in bottles for the active treatment period	Placebo will be presented in identical packaging, and stored/packaged the same as apremilast			
Unit Dose Strength(s)	30 mg	Placebo			
Dosage Level(s)	BID	BID			
Route of Administration	Oral	Oral			
Accountability	The amount dispensed, amount returned, date dispensed, date returned, and lot number of Investigational Product(s) is to be recorded on each subject's CRF(s).				
Dosing Instructions	Dosing will oc	cur as follows:			
	Day 1 AN	Day 1 AM: 10 mg			
	Day 2 AM	И: 10 mg			
	Day 2 Pl	Day 2 PM: 10 mg			
	Day 3 AM	И: 10 mg			
	Day 3 PN	Day 3 PM: 20 mg			
	Day 4 AM	Day 4 AM: 20 mg			
	Day 4 PN	Day 4 PM: 20 mg			
	Day 5 AM	Day 5 AM: 20 mg			
	Day 5 PN	Day 5 PM: 30 mg			
	Day 6 and there	Day 6 and thereafter AM: 30 mg			
	Day 6 and there	after PM: 30 mg			
Dosage Preparation	N	/A			

BID = twice daily; N/A = not applicable

^a Apremilast will be manufactured and packaged by Amgen and distributed using Amgen clinical study drug distribution procedures.

Protocol Number: 20200195

Date: 15 April 2022 Page 35 of 99

6.1.2 Other Protocol-required Therapies

There are no other protocol-required therapies.

6.1.3 Product Complaints

A product complaint is any written, electronic or oral communication that alleges deficiencies related to the identity, quality, durability, reliability, safety, effectiveness, or performance of a drug, combination product, or device after it is released for distribution to market or clinic by either (1) Amgen or (2) distributors or partners for whom Amgen manufactures the material. This includes all components distributed with the drug, such as packaging drug containers, delivery systems, labeling, and inserts.

This includes any investigational/non-investigational product(s), device(s) or combination product(s) provisioned and/or repackaged/modified by Amgen:

Any product complaint(s) associated with an investigational product(s), non-investigational products(s), devices(s), or combination product(s) supplied by Amgen are to be reported.

6.1.4 Excluded Treatments and/or Procedures During Study Period

Table 6-2. Excluded Treatments and/or Procedures During Study Period

Prohibited Treatment	Time Period for Exclusion
Strong cytochrome P450 3A4 (CYP3A4) enzyme inducers (eg, rifampin, phenobarbital, carbamazepine, phenytoin and St. John's Wort)	2 weeks or 5 times the half-life, whichever duration is longer, prior to randomization and until the end of active treatment
Granulocyte and monocyte adsorption apheresis	2 weeks prior to randomization until the end of active treatment
Topical therapies that could affect PPP or the efficacy evaluation (including, but not limited to, corticosteroids, retinoid, vitamin D3 derivatives, tacrolimus, antihistamine, antibiotics or traditional Chinese/Japanese herbal preparations).	2 weeks prior to randomization and during double-blind, placebo-controlled period; allowed after week 16 Note: Only use of topical antibiotics for the treatment after skin biopsy is permitted. Unmedicated skin moisturizer (eg, Vaseline) will be permitted as needed.
Conventional systemic therapies that could affect PPP or the efficacy evaluation (including, but not limited to corticosteroids, antihistamine, antibiotics, JAK inhibitors, 1,25-dihydroxy vitamin D3 and analogues, psoralens, sulfasalazine, hydroxyurea, dimethyl fumarate, biotin, or colchicine)	4 weeks prior to randomization until end of active treatment Note: Systemic antihistamines are allowed after week 16
Systemic therapy for PAO including, but not limited to bisphosphonates,	4 weeks prior to randomization and until end of active drug treatment period

Protocol Number: 20200195

Date: 15 April 2022 Page 36 of 99

immunosuppressants [eg, MTX, azathioprine, cyclosporine or 6-thioguanine, mercaptopurine, mycophenolate mofetil, tacrolimus]) and other biologics (eg, anti-IL1 antibody)

Note: Background stable doses of NSAIDs for treatment of PAO are permitted.

Page 1 of 2

Protocol Number: 20200195

Date: 15 April 2022 Page 37 of 99

Table 6-2. Excluded Treatments and/or Procedures During Study Period

Prohibited Treatment	Time Period of Exclusion	
Prolonged sun exposure or used tanning booths or other ultraviolet light sources	4 weeks prior to randomization and until the end of active treatment period	
Biologic therapy such as:		
TNFα or IL17 blockers (eg, adalimumab, brodalumab, certolizumab pegol, etanercept, golimumab, infliximab, ixekizumab, secukinumab, or biosimilars for each)	12 weeks or 5 times the half-life, whichever duration is longer, prior to randomization and until end of active treatment period. 24 weeks OR 5 times the half-life, whichever duration is longer, prior to randomization and until end of active treatment period.	
Anti-IL12 or anti-IL23 monoclonal antibodies such as guselkumab, ustekinumab or tildrakizumab and other biologics		
Phototherapy (ultraviolet B radiation [UVB] or psoralen ultraviolet A radiation [UVA])	4 weeks prior to randomization; allowed after week 16 during drug treatment period	
The following focal infection treatments for PPP (but not limited to):	24 weeks prior to baseline until the end of active treatment period	
Tonsillectomy for tonsils	Note: Dental therapy (non-invasive dental care [eg, scaling and root planning for	
Endodontic treatment for periapical pathosis	periodontal disease]) is permitted	
Periodontal surgery for moderate to severe periodontitis	throughout the study	
Systemic retinoids (eg, etretinate)	2 years prior to randomization for females of childbearing potential, 4 weeks prior to randomization for females of non-childbearing potential, and 6 months prior to randomization for males until end of active treatment period.	

Page 2 of 2

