4.1 Overall Design

The overall study design is described by a study schema in Section 1.2. The endpoints are defined in Section 3.

Approximately 170 subjects will be enrolled in the study, with subjects being randomized in a 1:1 ratio to 1 of 2 treatment arms: apremilast 30 mg BID or placebo. Subject

Protocol Number: 20200195

Date: 15 April 2022 Page 27 of 99

randomization will be stratified by a subject's rounded PPPASI total score (≤ 20/ 21 - 30/≥ 31) at baseline and baseline focal infection status (yes/no).

Randomized subjects will receive either apremilast 30 mg BID or placebo for 16 weeks, the duration of the double-blind placebo-controlled treatment period. During the active treatment period (week 16 to week 52), all subjects will receive apremilast 30 mg BID. The dose titration procedure (in line with the label) will be implemented for all subjects over a 5-day period at week 0 (the beginning of the double-blind placebo-controlled treatment period) and at week 16 (the beginning of the active treatment period) to mitigate potential gastrointestinal side effects and to maintain blinding.

After the final dose treatment, subjects will enter a **30-day** safety follow-up period. The total study duration per subject is **approximately** 60 weeks.

The primary analysis will be performed after the last subject has completed the week 16 visit (visit 8) or study discontinuation. An additional analysis will be conducted after all subjects have completed the week 24 visit (visit 10) or have been discontinued from the study. The final analysis will be conducted after all subjects have either completed or discontinued the study.

Approximately 45 sites in Japan are planned to participate in the study. Sites that do not enroll a subject within 6 months of site initiation may be closed.

Participants in this clinical investigation shall be referred to as "subjects". For the sample size justification, see Section 9.2.

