2.1 Objectives and Endpoints/Estimands

Objec	tives	Endpoints			
Prima	Primary				
•	To evaluate the efficacy of apremilast 30 mg twice daily (BID) compared with placebo in subjects with PPP	 Achieving at least 50% reduction from baseline in Palmoplantar Pustulosis Area and Severity Index (PPPASI) total score (PPPASI-50) at week 16 			
Seco	ndary				
•	To evaluate the efficacy of apremilast 30 mg BID compared with placebo in subjects with PPP	 Change from baseline in PPPASI total score at week 16 Change from baseline in Palmoplantar Pustulosis Severity Index (PPSI) total score at week 16 Change from baseline in subject's Visual Analogue Scale (VAS) assessment for PPP symptoms (pruritus and pain/discomfort) at week 16 Change from Baseline in Dermatology Life Quality Index 			
		(DLQI) total score at week 16			
•	To evaluate the safety and tolerability of apremilast 30 mg BID compared with placebo in subjects with PPP	 Treatment-emergent adverse events (TEAEs), serious TEAEs, and TEAEs of interest Clinically significant changes in body weight, vital signs, and laboratory abnormalities 			

Primary Estimand

The main estimand of primary interest for the primary efficacy endpoint (i.e., achievement of PPPASI-50 response defined as at least 50% reduction from baseline in PPPASI total score, at week 16) is defined in terms of the following attributes:

- The target population of interest is Japanese subjects with PPP defined through the inclusion/exclusion criteria.
- The primary endpoint is the achievement of PPPASI-50 response at week 16.
- Intercurrent events (IEs) are investigational product (IP) discontinuation due to lack of efficacy, adverse event, or protocol-prohibited medication use. A subject will be considered a treatment failure after any of the IEs.
- The summary measure is the difference between apremilast 30 mg BID group and placebo group in proportion of responders based on the intent-to-treat (ITT) population including all randomized subjects.

A missing value after any of the IEs will be imputed as non-responders, otherwise, will be imputed with a multiple imputation (MI) method. A non-missing value after any of the IEs will also be imputed as non-responders.

Secondary Estimand(s)

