8.3.2 Missing Post-Baseline Evaluation

In the primary endpoint analysis of PPPASI-50 response at week 16, the PPPASI-50 values will be imputed as non-responder for visits on and after a subject experiencing any of the IEs. The missing PPPASI-50 values due to other reasons will be imputed using MI method.

For the secondary endpoints (i.e., the change from baseline at week 16 in PPPASI total score, PPSI total score, subject's VAS assessment for PPP symptoms [pruritus and pain/discomfort], and DLQI total score), the corresponding endpoints' baseline value will

be assigned to the data on and after any of the IEs regardless of the observed data and no imputation will be applied to the missing data (PPPASI total score) due to other reasons. Similar approach will be applied to the other endpoints of responses and continuous variables, unless otherwise specified.

For safety data, missing post-baseline measurements/assessments will not be imputed.

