9.1 General Considerations

The ITT principle will be used in statistical analyses for efficacy endpoints. For the placebo-controlled period (Weeks 0-16), efficacy evaluations will be conducted using the ITT population defined as all randomized subjects. Statistical comparisons for placebo-controlled period in Primary Analysis (PA) will be made between the two treatment groups (placebo and apremilast 30 mg BID). For the active treatment period (Weeks 16-52), analysis for differences between the two groups will not be performed although summaries of each group will be provided.

Descriptive statistics will be presented for appropriate endpoints at specified time points. Specifically, summary statistics for continuous variables will include the number of subjects (n), mean, SD, median, the 25th (Q1) and 75th (Q3) percentiles, minimum, and maximum. For efficacy variables, standard errors (SEs) for estimates will be included, unless otherwise specified. Frequency summary for categorical variables includes counts and percentages.

Statistical inferences will be provided for analyses of primary, secondary and the exploratory efficacy endpoints. Unless specified otherwise, all statistical tests are 2-sided with a significance level of 0.05; no statistical inference and imputation will be conducted for analyses of safety endpoints.

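### Topical PPP therapies and systemic antihistamines are permitted after week 16, and the visible SAP has no rule for their use, so week 20–52 efficacy summaries may overstate response on apremilast alone

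*Protocol*

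**What the plan says.** **Permitted therapy.** Protocol 6.1.4, Table 6-2, gives the exclusion period for topical therapies that could affect PPP or its evaluation (corticosteroids, vitamin D3 derivatives, retinoids, tacrolimus and others) as "2 weeks prior to randomization and during double-blind, placebo-controlled period; allowed after week 16". The row for conventional systemic therapies keeps its ban to the end of active treatment, with one exception: "Systemic antihistamines are allowed after week 16". The phototherapy row reads "4 weeks prior to randomization; allowed after week 16 during drug treatment period".

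**Switch.** All subjects receive apremilast 30 mg BID from week 16 to week 52 (Protocol 4.1; SAP 3.1).

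**Failure rule.** SAP 2.1 states: "Intercurrent events (IEs) are investigational product (IP) discontinuation due to lack of efficacy, adverse event, or protocol-prohibited medication use". SAP 9.5.1 and 9.5.2 apply this to discontinuation before week 16. For everything else, SAP 8.3.2 sets a default: "Similar approach will be applied to the other endpoints of responses and continuous variables, unless otherwise specified".

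**Reporting after week 16.** PPPASI and PPSI are scored at weeks 20, 24, 32, 44 and 52, and the VAS at weeks 24, 32 and 52 (Protocol Table 1-1). For this period SAP 9.1 says "analysis for differences between the two groups will not be performed although summaries of each group will be provided". SAP 7.3 and 7.4 place the results in the week 24 supplemental analysis and the final analysis. The exploratory objectives in SAP 2.1 and the contents of Tables 9-3 and 10-1 cannot be read in the public copy.

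**Concomitant therapy.** Protocol 6.6.2 collects name, indication and start and stop dates. SAP 9.4.5 and 9.6.7 summarise concomitant medication for PPP by treatment group.

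**The concern.** A therapy that Table 6-2 allows after week 16 is not prohibited medication, and using it is not discontinuation of investigational product. It therefore triggers nothing in the visible failure rule. A subject who is a non-responder at week 16, starts a topical corticosteroid at week 18 and reaches PPPASI-50 at week 24 is summarised as a responder under the default in SAP 8.3.2. Antihistamines raise the same question for VAS pruritus.

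In the placebo group the two changes come together: apremilast starts and the restriction ends.

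The week 24 and week 52 summaries are what the trial will show on maintenance of effect and on response after the switch. The Amendment 1 rationale says the week 24 analysis was added, following requests from the Japanese agency, to supply at least six months of efficacy and safety data. A reader of those rates will want to know how far they depend on other PPP treatment. The planned concomitant-medication tables count users, but they state no split at week 16 and no link to response.

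**Working it through.** **1. The plan's own figure.** Inputs from Protocol 9.2 and SAP 3.2: 40% versus 65%, 85 per group, two-sided alpha 0.05, stated power 90%.

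- Pooled standard error under the null: √(2 × 0.525 × 0.475 / 85) = 0.0766.
- Standard error under the alternative: √((0.40 × 0.60 + 0.65 × 0.35) / 85) = 0.0742.
- Power = Φ((0.25 − 1.96 × 0.0766) / 0.0742) = Φ(1.35) = 91.1%.

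With 5% dropout (80.75 per group) power is 89.6%. The stated 90% reproduces. It concerns week 16 only, and the documents give no figure for weeks 20–52.

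**2. Possible excess after week 16.** None of these inputs for weeks 20–52 is in the documents:

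- p = response rate on apremilast alone, set to the 65% planning value for week 16;
- u = share of non-responders who start a newly permitted therapy, 10% to 60%;
- r = share of those who then reach PPPASI-50, 20% to 50%.

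Reported rate = p + (1 − p) × u × r.

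| u | r | Excess (points) | Reported rate |
|---|---|---|---|
| 10% | 20% | 0.35 × 0.10 × 0.20 = 0.7 | 65.7% |
| 20% | 40% | 0.35 × 0.20 × 0.40 = 2.8 | 67.8% |
| 40% | 40% | 0.35 × 0.40 × 0.40 = 5.6 | 70.6% |
| 60% | 50% | 0.35 × 0.60 × 0.50 = 10.5 | 75.5% |

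**3. Yardstick.** The SAP summarises each group, so the relevant n is 85: √(0.65 × 0.35 / 85) = 5.2 points. The excess runs from 0.7 / 5.2 = 0.13 to 10.5 / 5.2 = 2.0 standard errors.

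**4. What the supplementary summary would do.** Suppose a share v of subjects who respond on apremilast alone also add a therapy. Counting all add-on users as non-responders gives 65% × (1 − v): 58.5% at v = 10% and 52.0% at v = 20% (again assumed values). This lies below the apremilast-alone rate, while the planned summary lies at or above it if add-on therapy does not worsen response. The two summaries then bracket the quantity of interest.

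**The case against.** **The rule may exist where it cannot be read.** The week 20–52 endpoints and methods would sit in Tables 9-3 and 10-1, and SAP 8.3.2 yields to anything specified elsewhere. This stands. The point rests on the visible default, and redacted text is not a gap in the plan. If a rule is there, the sponsor need only point to it.

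**The planned summary is legitimate.** The period is descriptive, has no between-group comparison, and no visible text claims that the rates belong to apremilast alone. Outcomes under permitted background care are a sensible thing to report. This also stands, so the planned summaries should be kept. What is missing is a label and a companion result.

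**A reader might infer that lifting the restriction is what stops switchers' gains being credited to apremilast.** The documents do not support that. There is no control after week 16, so those gains could not be attributed causally even with no add-on use.

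**A reader might also infer that the rates are certainly inflated, and by a known amount.** That is not supported either. Uptake and benefit are unknown, and the documents give reasons for a small effect: subjects must have had an inadequate response to topical treatment (Protocol 5.1), and the evidence for topical therapy and phototherapy in moderate to severe disease is described as limited (Protocol 2.1). On the other side, Protocol 2.2.2 describes topical therapy as basic treatment, so some uptake is plausible.

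**Subject listings allow a link.** SAP 9.4.5 and 9.5 provide listings of medication and efficacy data. A reader holding both could join them, but readers of the summary tables could not.

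**Conclusion.** The concern holds in a limited form. Under the visible default, the week 20–52 PPPASI, PPSI and VAS summaries describe apremilast with or without newly permitted therapy, and may overstate response on apremilast alone. The illustrated range of 0.7 to 10.5 points rests wholly on assumed uptake and conversion. Its lower end is negligible beside the standard error of 5.2 points, and its upper end is about twice that error. The conclusion is conditional on the redacted tables containing no different rule.

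Nothing here touches the primary endpoint, the fixed-sequence secondary endpoints or the type I error, all of which are fixed at week 16. It is an inexpensive improvement to the descriptive long-term results.

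The conclusion does not rely on phototherapy. The phototherapy row of Table 6-2 conflicts with the row that bars other ultraviolet light sources until the end of the active treatment period, and with the inclusion criterion in Protocol 5.1 under which subjects agree to avoid ultraviolet sources to the palms and soles during the study. It cannot simply be read as released at week 16.

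**What to change.** 1. Keep the planned week 20–52 summaries and label them as including permitted add-on therapy.
2. In SAP 8.3.2 and 9.1, add one supplementary summary per endpoint for weeks 20–52. In it, visits on and after the first post-week-16 use of a therapy that Table 6-2 barred before week 16 are set to non-response, or to the baseline value for continuous scores. For VAS pruritus, count systemic antihistamines among these therapies.
3. Beside it, report the number and percentage of add-on users by visit and treatment sequence.
4. Describe the supplementary result as a conservative bound. It also reclassifies subjects who had already responded before adding therapy, and it gives no causal attribution for switchers.
5. If Tables 9-3 or 10-1 already contain a rule, refer to it in 8.3.2 instead.
6. Separately, reconcile the phototherapy row, the row on other ultraviolet light sources and the inclusion criterion on ultraviolet exposure. Whether phototherapy enters the list in item 2 follows from that.

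Items 1 to 5 cost SAP wording and one extra table per endpoint, using start dates already collected under Protocol 6.6.2. They need no new data and leave patient care and the week 16 tests unchanged. The downside is a second set of long-term rates that will be lower than the first.
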